 - An estimated glomerular filtration rate (eGFR) based on the most recent available serum creatinine of <40 mL/min/1.73 m² if greater than 2 year of age. eGFR will be calculated using the *Bedside Schwartz Equation:* eGFR (mL/min/1.73 m²) = (0.413 x height) / S_{Cr}, with height measured in cm, and serum creatinine (S_{Cr}) in units of mg/dL.
 - Children with an eGFR of <40 mL/min/1.73 m² will not be enrolled, unless <24 months of age in which case a cut off of <30 ml/min/1.73 m2 will be used due to age-based differences in normal eGFR. Normal eGFR of <60 ml/min/1.73 m² is common in children <12 months, and a normal eFGR <40 ml/min/1.73 m² is common in infants <3-6 months.
 - The creatinine should be measured using the IDMS (Isotopic Dilution Mass Spectrometry) technique to monitor the eGFR if available. Other methods are allowed but are not preferred. Laboratory testing using other methods will not be used to monitor the eGFR.
- Have any of the following specific Hematologic abnormalities on screening laboratory tests (Appendices 10, 11, 12):
 - Hemoglobin <7 mg/dL (70 g/L). In infants <2 mo of age, 8 mg/dL will be used as a threshold
 - Neutropenia (absolute neutrophil count [ANC] <500 cells/µL)
 - CD4 <250 cell/µl on lymphocyte subset testing (where Absolute CD4 count=Absolute CD3/CD4 count=CD3/CD4 count=CD4 count=Absolute CD3+CD4+ cells)
 - Thrombocytopenia (platelets <30,000/µL). Patients who are on

anticoagulation or having a history of life-threatening bleeding should be excluded if platelet count is <50,000/µL

- Have any of the following infectious risks:
 - Evidence of active infection, at the time of entry or during the screening period, that in the opinion of the investigator, would pose an unacceptable risk for participating in the study
 - Ongoing or incompletely treated severe or systemic infection, excluding cellulitis/osteomyelitis that is felt to be attributable to AGS
 - Have had symptomatic herpes zoster infection within 12 weeks prior to entry or during the screening period
 - Have a history of disseminated/complicated herpes zoster (for example, multidermatomal involvement, central nervous system involvement or systemic involvement including hepatitis or pneumonitis)
 - Have a history of active hepatitis B, hepatitis C, or human immunodeficiency virus (HIV)
 - Have had household contact with a person with active tuberculosis (TB) and did not receive appropriate and documented prophylaxis for TB

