4.4.2 Initial Treatment and Dose Escalation

Baricitinib will be dosed by patient age, weight range and eGFR. See Appendix 3 for the dosing schedule for patients with eGFR \geq 60 mL/min/1.73 m² or normal eGFR for patients age <24 months (eGFR \geq 60 mL/min/1.73 m²). eGFR will be calculated using the *Bedside Schwartz Equation:* eGFR (mL/min/1.73 m²) = (0.413 x height) / S_{Cr}, with height measured in cm, and serum creatinine (S_{Cr}) in units of mg/dL. The creatinine should be measured using the IDMS (Isotopic Dilution Mass Spectrometry) technique to monitor the eGFR if available. Other methods are allowed but are not preferred. Laboratory testing using other methods will not be used to monitor the eGFR. Tolerance will be judged by stability or improvement in hematology and chemistry laboratory test results collected as specified in Study Schedule (Appendices 1 and 2). See Appendix 4 for the dosing schedule for patients with eGFR 30 - <60 mL/min/1.73 m²).

Patients must receive a dose for at least 72 hours before a dose escalation can occur. Safety laboratory data will be assessed according to the Study Schedule (Appendices 1 and 2).

Every effort should be made to follow the dose escalation schedule shown in Appendices 3 and 4. However, if a patient's condition warrants an accelerated dose escalation schedule, dose reduction, interruption, or discontinuation, this may be allowed after review of the patient's clinical data and consultation with the subinvestigators. Additionally, in the event of AEs possibly attributable to the study drug, the dose may need to be reduced. These decisions should be taken following documented consultation, and agreement between the investigator and subinvestigators, and approval from the IRB prior to initiating the dose modification. Only in emergency situations will the investigator take subsequent dose restarts or increments after review of clinical data, documented agreement between the investigator and subinvestigators, and notification of the IRB.

Attention will be given to concomitant medications, in particular those that are exclusion criteria (Appendix 16).

Where needed, clinical pharmacists will be contacted about the need for dose adjustment and for guidance related to concomitant therapies that must be used with caution.

In the event that it is necessary to contact a clinical pharmacist, the study team can page the 24/7 on-call clinical pharmacist.

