Pharmacokinetic Sampling: Blood samples will be collected to determine baricitinib concentrations. Samples will be collected after beginning baricitinib therapy and at each dose increase at the time points shown in the Study timeline and may be collected at each study visit for safety monitoring. In these cases, PK sampling will occur at least 72 hours after dosing changes or at the next visit. PK testing may include a single measurement at 1.5 hours, or a full PK series at baseline, 1.5 hours and 4 hours post dose, and may include several doses during the day (eg morning and afternoon dose). For PK series, an IV will be placed. For single PKs, these will be drawn with the safety laboratory monitoring. PK samples may be banked for later analysis. As PK data become available, dosing adjustments may be required. Finally, changes in a subject's weight or renal function may require dose changes as the individual falls within different categories in the tables in Appendices 3 and 4. For example, this may occur in a child under 1 year of age with rapid weight gain.

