BID = twice daily, eGFR = estimated glomerular filtration rate, QID = 4 times daily, TID = 3 times daily.

a If there was a change in the patient's weight during the study, this would place the patient in a different weight range.

b Based on adult patient data as there is little data available in pediatric patients.

c. For the purposes of this protocol, we will define age based parameters for eGFR as follows: Normal renal function not requiring dose adjustments if: >12 months: At least a GFR of >60 ml/min/1.73 m2. <12 months: A GFR of >40 ml/min/1.73 m2. Patients will be excluded from enrollment if baseline eGFR was <30 ml/min/1.73 m2

The creatinine should be measured using the IDMS (Isotopic Dilution Mass Spectrometry) technique to monitor the eGFR if available. Other methods are allowed but are not preferred. Laboratory testing using other methods will not be used to monitor the eGFR.

The population PK analysis was updated including data from 71 juvenile and adolescent patients with Chronic Atypical Neutrophilic Dermatosis with Lipodystrophy and Elevated Temperature (CANDLE), CANDLE related disorders, STING-associated vasculopathy with onset in infancy (SAVI), and Aicardi-Goutières syndrome (AGS). The analysis has shown that while kidney function, as expressed by estimated GFR, is a statistically significant patient cofactor of the PK characteristics of baricitinib in this multi-disease patient population, the effects of eGFR on the kinetics of this patient population were not clinically relevant as they relate to dosing and did not support dose adjustment for patients with eGFR less than 120 mL/min/1.73 m².

Appendix 4. Dose Escalation Schedule for Patients with eGFR 30- <60 mL/min/1.73 m2 or for Age <24 Months with abnormal eGFR (see footnote below^c)

If a change in the patient's weight during the study would place the patient in a different weight range changes over time are permitted.

		Morning Dose	Noon Dose	Afternoon Dose	Evening Dose	Total Daily Dose	Dosing Frequency
eGFR 30 - < 60 mL/min/ *	1.73 m ^{2b}						I
10-< 20 kg	Initial	1 mg	1 mg	0 mg	1 mg	3 mg	TID
	Escalation 1	1 mg	1 mg	1 mg	1 mg	4 mg	QID
20-< 40 kg	Initial	2 mg	-	_	1 mg	3 mg	BID
	Escalation 1	2 mg	_	_	2 mg	4 mg	BID
≥ 40 kg	Initial	2 mg	_	_	2 mg	4 mg	BID
	Escalation 1	3 mg	-	_	3 mg	6 mg	BID

BID = twice daily, eGFR = estimated glomerular filtration rate, QID = 4 times daily, TID = 3 times daily.

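### Section 4.4.2 and footnote c to Appendices 3 and 4 define normal eGFR differently, so an infant under 12 months with eGFR above 40 and below 60 is sent to two dose tables; Appendix 4 as printed also has no row below 10 kg

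*Combined protocol and SAP*

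**What the plan says.** Section 7.1.3 ties dosing to Appendices 3 and 4. Appendix 3 is for eGFR of at least 60, or normal eGFR under 24 months of age. Appendix 4 is headed "Dose Escalation Schedule for Patients with eGFR 30- <60 mL/min/1.73 m2 or for Age <24 Months with abnormal eGFR".

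What counts as normal is stated twice. Section 4.4.2 sends to Appendix 3 those with "normal eGFR for patients age <24 months", and its bracket then defines this as at least 60; eGFR from 30 to below 60 goes to Appendix 4. Footnote c, printed under both tables, says that no dose adjustment is needed at "<12 months: A GFR of >40 ml/min/1.73 m2", and above 60 for those older than 12 months.

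Entry is open from 1 month of age and 4.5 kg (Section 3.3.2). Section 3.3.3 excludes children with eGFR below 40 "unless <24 months of age in which case a cut off of <30 ml/min/1.73 m2 will be used". It explains that a normal eGFR below 60 is common before 12 months, and that one below 40 "is common in infants <3-6 months". After entry, Section 4.4.2 notes that changes in "weight or renal function may require dose changes as the individual falls within different categories in the tables".

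Appendix 4 as printed has three weight bands: 10 to <20, 20 to <40, and 40 kg or more. Appendix 3 has a further band below 10 kg.

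**The concern.** For an infant in the disputed eGFR range, two people following the protocol can prescribe from different tables, and both can cite it. That is a dosing inconsistency in the youngest patients. It also means that the dose received for a given weight and eGFR depends on which page was consulted.

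The missing weight band raises a different problem. A child under 10 kg can satisfy the entry criteria, be classed as having abnormal eGFR under either definition, and then find no starting dose. A treated child under 10 kg whose eGFR falls into the Appendix 4 range has no row to move to. Section 1.1 expects the greatest benefit when treatment starts as early as possible, so a clear starting dose matters most in this group.

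**Working it through.** **1. Plan's own figures.** Adding the component doses in each row reproduces all 15 printed daily totals (9 in Appendix 3, 6 in Appendix 4). The starting doses are:

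| Weight | Appendix 3 start | Appendix 4 start |
|---|---|---|
| below 10 kg | 1+1+0+1 = 3 mg | no row printed |
| 10 to <20 kg | 2+2+0+2 = 6 mg | 1+1+0+1 = 3 mg |
| 20 to <40 kg | 3+0+3 = 6 mg | 2+1 = 3 mg |
| 40 kg or more | 4+4 = 8 mg | 2+2 = 4 mg |

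**2. The two rules applied to eligible children under 24 months.**

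| Age | eGFR | Section 4.4.2 | Footnote c |
|---|---|---|---|
| <12 months | 30 to 40 | Appendix 4 | Appendix 4 |
| <12 months | >40 to <60 | **Appendix 4** | **Appendix 3** |
| <12 months | 60 or more | Appendix 3 | Appendix 3 |
| 12 to <24 months | 30 to <60 | Appendix 4 | Appendix 4 |
| 12 to <24 months | above 60 | Appendix 3 | Appendix 3 |

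Apart from the boundary value of exactly 60 after 12 months, the rules disagree in one cell only. Spot checks at ages 3, 6 and 11 months gave the conflict at eGFR 45, 50 and 59, and agreement at 32, 38 and 65.

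**3. Dose consequence in that cell.** At 10 to <20 kg the starting dose is 6 or 3 mg/day, and the first escalation 8 or 4 mg/day: ratios of 6/3 = 2 and 8/4 = 2. Below 10 kg it is 3 mg/day (escalating to 4) or nothing printed. The documents give no weight distribution for infants, so how these two consequences divide is not known.

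**4. What puts a child in that cell.** The protocol's Bedside Schwartz formula is eGFR = 0.413 × height / creatinine. Assume a length of 65 cm: 0.413 × 65 = 26.845. eGFR is 60 at creatinine 26.845/60 = 0.45 mg/dL and 40 at 26.845/40 = 0.67 mg/dL. The conflict then covers creatinine between about 0.45 and 0.67 mg/dL. This shows where the boundary lies, not how often it is met.

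**5. Who falls below the printed Appendix 4 rows.** Under both definitions, a child under 10 kg has no row if aged under 12 months with eGFR 30 to 40, or 12 to <24 months with eGFR 30 to <60. Following Section 4.4.2 adds infants under 12 months with eGFR above 40 and below 60.

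**6. Frequency.** Table 1 (Safety Measures) covers 35 patients. Before study, eGFR was grade 0 in 29 and grade 1 in 6 (29 + 6 = 35); on study, 19 and 16 (19 + 16 = 35). None exceeded grade 1. The grade cut-offs are not printed there, so these counts cannot be mapped to an eGFR of 60 or split by weight.

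**The case against.** **Footnote c is meant to govern.** It presents itself as the definition for the protocol and sits under both tables, one of which Section 4.4.2 tells the reader to use. The bracket in Section 4.4.2 also makes its own age clause redundant, which suggests a drafting slip. This is probably right, and it is why the correction is short. But Section 4.4.2 does not defer to the footnote, and it is the section that tells staff how to choose a table.

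**The missing row may be a reading artefact.** The text copy of these tables is visibly clipped (the eGFR label in Appendix 3 has lost its first letters), and Appendix 14 lists a 1 mg twice-daily starting regimen that matches no printed row. Against that, the three Appendix 4 bands are complete with no stray fragment, and Appendix 14 lists other regimens found in neither table (3 mg four times daily, 4 mg three times daily). The question stays open until the PDF is checked. The conflict of definitions rests on running text and does not depend on it.

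**There is a fallback.** Section 4.4.2 provides for consultation, IRB-approved dose modification, pharmacist advice and PK-guided adjustment. These are real routes, so it would be too strong to say that such a child could not be treated. None of them names a dose.

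**Renal adjustment may not matter.** A reader might infer that infants dosed from Appendix 3 would be overexposed. The documents do not support this. The population PK note, based on 71 juvenile and adolescent patients, says that eGFR effects "were not clinically relevant as they relate to dosing and did not support dose adjustment for patients with eGFR less than 120", and footnote b describes the renal tier as "Based on adult patient data as there is little data available in pediatric patients". Yet Appendix 4 halves the starting dose in every band it prints, so the protocol does not say which position holds below 10 kg. For the same reason, halving the Appendix 3 dose for that band would be extrapolation.

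**Entry weight.** A reader might also see a gap between the 4.5 kg entry weight and an Appendix 3 band that reads as starting at 5 kg. The clipped left edge explains that figure equally well, so it is not evidence of an error.

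**Conclusion.** The conflict of definitions is established. It is confined to infants under 12 months with eGFR above 40 and below 60, a range that Section 3.3.3 treats as ordinary at that age. There it produces a two-fold difference in starting dose at 10 to <20 kg, and a choice between 3 mg/day and no printed dose below 10 kg.

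The absent Appendix 4 row below 10 kg is established only for the text as printed, and is conditional on the PDF. If confirmed, it affects children whom the entry criteria deliberately admit.

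Neither part shows harm. The number of children affected cannot be computed and is probably small, given no eGFR abnormality above grade 1 in the 35 tabulated patients. The case for acting is that dosing instructions should give one answer and the correction is cheap.

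**What to change.** **First, regardless of the PDF.** Replace the bracket in Section 4.4.2 with footnote c's age-based definition: *normal eGFR not requiring dose adjustment is >40 mL/min/1.73 m² under 12 months, and ≥60 at 12 months or older*. Using ≥60 matches the Appendix 3 title and settles the value of exactly 60. Limit the 30 to <60 range in the Appendix 4 sentence of Section 4.4.2, and in the Appendix 4 title, to age 12 months or older; otherwise both still capture the same infants.

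**Second, check Appendix 4 in the PDF.** If there is no row below 10 kg, do one of the following:
- add a pharmacology-approved row below 10 kg, in whole 1 and 2 mg tablets; or
- if the sponsor relies on the population PK analysis, state that patients under 10 kg in the Appendix 4 eGFR range receive the Appendix 3 dose for their weight.

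Either option covers both entry and a later fall in eGFR.

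**Cost.** One written amendment, with IRB approval and FDA notification (Section 9.8.7), and input from pharmacology for the second part. If the PK analysis is right, a reduced row could under-treat some infants; the Appendix 3 option avoids that but sets the adult-based renal tier aside at low weight. Keeping the >40 threshold also leaves some very young infants with a physiologically normal eGFR below 40 classed as abnormal, so the second part matters most for them.

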Appendix 6. Patient Daily Diary for AGS infants 0-6 months

Appendix 7. Patient Daily Diary for AGS > 6 months

Age		6+ months		
If G tube: poor Medications:	feeding and re	egurgitation score maximum Time medication was administered:		
weatcations:	Lilly	Time medication was administered:		
System	categories	Signs and Symptoms	Yes/No	Score
	ity	Able to perform all activities of daily living or age appropriate milestones independently with no restriction		0
	sabil	Able to participate in the following with some level of disability: ambulation, communication or fine motor tasks at an age appropriate level		0
	ic di	Requires functional or equipment support for any of the following: ambulation, communication or fine motor tasks at an age	choose one of	0
	golo:	appropriate level	these	0
	Neurologic disability	Dependent for all activities of daily living and unable to ambulate, communicate or perform fine motor tasks at an age appropriate level even with support		0
		Cries but easily consolable		0
	Crying	Excessive or high-pitched cry inconsolable for >2 minutes OR intermittently for <10 min	choose one of	0
	Cry	Excessive or high-pitched cry inconsolable for >2 minutes AND intermittently for <10 min	these	0
		Excessive or high-pitched not consolable (cries >10 mins)		0
	Length of uninterrupted sleep	Sleeps >6 hours continuously during night		0
ces	Length of interrupt sleep	Sleeps 4-5 hour continuously during night	choose one of	0
rban	Ler nint s	Sleeps 2-3 hours continuously during night	these	0
istu		Sleeps <2 hours continuously during night		 
em c	Excessive irritability	no irritability consoling calms individual in <6 minutes	choose one of	0
syst	xces ritab	consoling calms individual in 6-15 minutes	these	0
snov	шË	consoling calms individual in >15 minutes or not at all		0
Central nervous system disturbances		No startle reflex		0
ntra		Mild startle to noise	choose one of	0
S		Strong startle reflex with noise	these	0
		Strong startle reflex with noise including face grimacing, blinking and repeated jerks of arms Any startle without noise		0
				0
		No tremors (shaking, jittering, or shivering movements of the extremities that are not seizures)	choose one of	0
		Tremors when disturbed (awoken from sleep, moved, or stimulated)	these	0
		Tremors when undisturbed		0
		No tone issues	choose one of these	0
		Increased or decreased muscle tone (excessive stiffness or floppiness)	these	0
	Generalized seizure	No convulsions or seizures	choose one of	0
			these	
	ğ	Experienced convulsions or seizures		0
	ki l	No fever (temperature less than 98.9 F)	choose one of	0
	Fever	Low grade fever: 99 - 101 F (37.2-38.3 C)	these	0
		Fever > 101.1 F (>38.4 C)		0
		No feeding issues	choose one of	0
		Poor feeding (infrequent/uncoordinated suck or dependent on g-tube feeding)	these	0
			choose one of	
		No regurgitation/vomiting Regurgitation/vomiting	these	0
ł	52	InderPretroni Annucli B		 
e	Skin findings body	Skin findings: no skin problem	choose one of	0
Other	n findi body	Skin findings: red patches which fade when pressed with fingers	these	0
	Ski	Skin findings: red patches not fading when pressed with fingers Skin findings: chronic discoloration		0
	Sg °'			
	Skin findings hands, face, ears	Skin findings: no skin problem		0
	in fir ands ea	Skin findings: red patches which fade when pressed with fingers Skin findings: red patches not fading when pressed with fingers	these	0
	sk hi	Skin findings: chronic discoloration		0
				0
		Skin findings: no skin problem in any location Skin findings: red patches which fade when pressed with fingers in any location	choose one of	0
		Skin findings: red patches which hade when pressed with higers in any location Skin findings: red patches not fading when pressed with fingers in any location	these	0
		Skin findings: chronic discoloration in any location		0

Appendix 8. Clinical Laboratory Tests

Hematology^{a,b,c}

Hemoglobin Hematocrit Erythrocyte count (RBC) Mean cell volume (MCV) Mean cell hemoglobin concentration (MCHC) Leukocytes (WBC) Reticulocyte Absolute counts of: Neutrophils, segmented Neutrophils, juvenile (bands) Lymphocytes Monocytes Eosinophils Basophils Platelets Cell Morphology Lymphocyte subset testing lgG

Lipid^e

Total cholesterol (TC) Low-density lipoprotein (LDL) High-density lipoprotein (HDL) Triglycerides

Urinalysis^{a,b,f}

Color Specific gravity pH Protein Glucose Ketones Bilirubin Urobilinogen Blood Leukocyte esterase Nitrite

Serum Chemistry^{a,b} Sodium Potassium Total bilirubinc Direct bilirubinc Alkaline phosphatase Alanine aminotransferase (ALT/SGPT)^c Aspartate aminotransferase (AST/SGOT)^c Blood urea nitrogen (BUN)^c Creatinine^c Calcium Glucose Albumin Total protein Creatine phosphokinase (CPK) Uric acid Gamma glutamyl transferase (GGT) Aldolased **INR**^k PT^k

Other Tests^a

Hepatitis B Surface antigen (HBsAg)⁹ Anti-Hepatitis B Core antibody (HBcAb)^g Hepatitis B Surface antibody (HBsAb)^g Hepatitis B Virus DNA^g Human immunodeficiency virus (HIV)^g Hepatitis C antibodyh Thyroid-stimulating hormone (TSH) Thyroxine (T4) Pregnancy Testing QuantiFERON®-TB Gold^{9,j} Baricitinib serum concentration BK virus PCR in plasma BK virus PCR in urine EBV PCR in plasma-quantitative CMV PCR in plasma-quantitative HSV IgG and IgM IGF-1 Vitamin D Cystatin C

Abbreviations: PPD = purified protein derivative; RBC = red blood cells; SGOT = serum glutamic oxaloacetic transaminase; SGPT = serum glutamic pyruvic transaminase; TB = tuberculosis; WBC = white blood cells.

- a. Assayed by local clinical laboratory.
- b. Unscheduled blood chemistry, hematology, and urinalysis panels may be performed at the discretion of the investigator.
- c. If a telephone visit is performed, lab samples should be obtained locally and the required labs to be reported are: total bilirubin, direct bilirubin, alanine aminotransferase (ALT), aspartate aminotransferase (AST), blood urea nitrogen (BUN), creatinine, and all hematology as listed
- d. Perform if inflammatory myositis is present.
- e. Lipid profile.
- f. Microscopic examination of sediment performed only if abnormalities are noted on the routine urinalysis.
- g. Test required at Visit 1 only to determine eligibility of patient for the study.
- h. A positive hepatitis C antibody result will be confirmed with a positive hepatitis C virus result.
- i. For all women of childbearing potential, a serum pregnancy test will be performed at Visit 1 and a urine pregnancy test (local laboratory) will be performed at Visit 2 to determine study eligibility. At subsequent visits, a urine pregnancy test will be performed.
- j. The QuantiFERON®-TB Gold test is the preferred alternative to the PPD test for the evaluation of TB infection, and it may be used instead of the PPD test and may be read locally. If the QuantiFERON®-TB Gold test is indeterminate, 1 retest is allowed. If the retest is indeterminate, then the patient is excluded from the study, unless the DSMB rules that the finding is likely related to underlying autoimmunity in AGS and not to TB infection.
- k. At baseline only.

